VP-VLY-686-2401 Confidential

Motion Sifnos: A Randomized, Double-Blind, Placebo-Controlled Study to Investigate the Efficacy of Tradipitant in Subjects Affected by Motion Sickness during Travel

Document Type:	Clinical Study Protocol
Sponsor:	Vanda Pharmaceuticals Inc. [name]
Study Product:	tradipitant (VLY-686)
Protocol Number:	VP-VLY-686-2401
Study Phase:	II
IND Number:	141315
NCT Number:	NCT03772340

Date: 03 18 2019 **Status:** Final

Name of Sponsor/Company:

Vanda Pharmaceuticals Inc.

Name of Investigational Product:

Tradipitant/VLY-686

Name of Active Ingredient:

Tradipitant/VLY-686

Title of Study: Motion Sifnos: A randomized, double-blind, placebo-controlled study to investigate the efficacy of tradipitant in subjects affected by motion sickness during travel

Study Center(s): 1

Studied Period:	Phase of Development:
First subject enrolled: December 2018	Phase II
Estimated study duration: Four months	

Number of Subjects (planned): Approximately 150 affected subjects will be randomized and assigned to tradipitant 170 mg or placebo in a 1:1 ratio. Treatment assignments will be made according to a randomization schedule. Vehicle travel assessment will occur either in a motor vehicle (2A) or a boat (2B).

Diagnosis and Main Criteria for Inclusion: Adult males or females aged 18-75, inclusive, with a history of motion sickness who meet inclusion criteria.

Investigational Product, Dosage and Mode of Administration: Tradipitant 170 mg PO or placebo once approximately 60 minutes before entering the vehicle.

Duration of Treatment: If motor vehicle travel, one drive lasting approximately 120-240 minutes. If boat travel, one trip lasting approximately 90-300 minutes on the moving vessel.

Reference Therapy, Dosage and Mode of Administration: Placebo capsules will be provided in size and appearance identical to those containing tradipitant and will be administered orally.

Primary Objectives:

1. To assess the effects of tradipitant 170 mg on the symptoms of motion sickness during vehicle travel as measured by the MSSS.

Secondary Objectives:

- 1. To assess the effects of tradipitant 170 mg on the symptoms of motion sickness as measured by subjective parameter MSAQ.
- 2. To assess the effects of tradipitant 170 mg on the symptoms of motion sickness as measured by subjective parameter LTMSQ.
- 3. To assess the effects of tradipitant 170 mg on the symptoms of motion sickness as measured by subjective parameter SDQ.
- 4. To assess the effects of tradipitant 170 mg on the symptoms of motion sickness as measured by subjective parameter PGI-S.
- 5. To assess the effects of tradipitant 170 mg on the symptoms of anxiety as measured by STAI-6.
- 6. To assess the safety and tolerability of a single oral dose of tradipitant 170 mg.

Overall Design: This is a randomized, double-blind placebo-controlled trial to investigate the efficacy and safety of a single 170 mg oral dose of tradipitant in motion sickness affected male and female subjects during vehicle travel.

The screening phase will consist of the subject taking the motion sickness eligibility questionnaire (MSEQ) to assess their susceptibility to motion sickness. Following this questionnaire, the subject will be interviewed to understand their history of motion sickness. If the subject meets pre-defined criteria as being eligible based on the motion sickness eligibility questionnaire and interview, they will proceed to the next step of a screening visit at a clinical site with a physician and simultaneously a lab visit for a blood draw. If the subject passes the medical visit screen and blood draw based on inclusion and exclusion criteria they will proceed to the evaluation phase.

Eligible subjects will be randomized 1:1 to tradipitant 170 mg or placebo. Eligible subjects will be instructed to take tradipitant 170 mg or placebo approximately 60 minutes prior to entering the vehicle. Vehicle travel assessment will occur either in a motor vehicle (2A) or boat (2B). Subjects will be driven on a pre-determined route for approximately 120-240 minutes during motor vehicle travel or approximately 90-300 minutes during boat travel. The MSSS questionnaire will be completed approximately every 30 minutes of vehicle travel and the STAI-6 will be completed at the beginning of vehicle travel, prior to drug administration.

After the completion of the vehicle travel, subjects will complete several questionnaires including a motion sickness severity scale questionnaire (MSSS), a travel questionnaire for the subject to assess the likelihood of their travel experience to induce motion sickness based on experience scored from 1-9 (LTMSQ), a motion sickness assessment questionnaire (MSAQ), a questionnaire to record the duration of symptoms (SDQ), the 6-item Spielberger State-Trait Anxiety Inventory (STAI-6), and the Patient Global Impression of Severity Questionnaire (PGI-S). All questionnaires will be submitted for analysis. Subjects will then return for an EOS visit within 7 days of visit 2.

Statistical Methods: Motion sickness symptoms will be assessed by the MSSS questionnaire, with the other questionnaires serving as secondary endpoints. Motion sickness symptoms as measured by MSSS will be assessed by analysis of variance with the treatment group, vehicle, and site, if more than one site, as main effects. The primary efficacy analysis will be based on the ITT population. The statistical analyses will be detailed in the statistical analysis plan.

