1.2. Statistical Methods and Analysis Plan

1.2.1. General

This section describes the planned statistical analyses in general terms. A complete description of the methodology will be specified in a statistical analysis plan (SAP), which will be finalized prior to unblinding. Any changes in the statistical methods described in this protocol that occur prior to unblinding will be documented in the statistical analysis plan and will not require a protocol amendment.

Statistical hypothesis testing will be performed at two sided alpha level of 0.05. For continuous variables, population size (N for sample size and n for available data), the mean, the standard deviation (SD), the median, the minimum and maximum values will be tabulated. For categorical variables, population size and frequencies in each category will be tabulated.

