1.3. Efficacy Data Analysis

1.3.1. Primary Outcome and Methodology

The primary endpoint is motion sickness severity assessed by the MSSS questionnaire. The primary analysis method is ANOVA with the treatment group, vehicle, and site, if more than one site, as main effects. The primary efficacy analysis will be based on the ITT population.

The statistical analyses will be detailed in the statistical analysis plan (SAP).

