1.3.2. Secondary Efficacy Analysis

The secondary endpoints from other questionnaires (MSAQ, SDQ, LTMSQ, STAI-6, PGI-S) will be analyzed in the same way as the primary endpoint. Other statistical methods may also be used as deemed appropriate. The details will be provided in the SAP.

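### The first STAI-6 reading has contradictory timing and no stated role in the anxiety analysis

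*Combined protocol and SAP*

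**What the plan says.** **Timing of the first reading.** Synopsis, Overall Design: "the STAI-6 will be completed at the beginning of vehicle travel, prior to drug administration".

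**Timing of the dose.** The same section: "Eligible subjects will be instructed to take tradipitant 170 mg or placebo approximately 60 minutes prior to entering the vehicle". The Synopsis entry on dosage and mode of administration agrees: a single dose, "once approximately 60 minutes before entering the vehicle".

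**Second reading.** Overall Design lists STAI-6 again among the questionnaires completed after travel. It is the only measure named for secondary objective 5 (anxiety).

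**Analysis.** Section 1.3.2: "The secondary endpoints from other questionnaires (MSAQ, SDQ, LTMSQ, STAI-6, PGI-S) will be analyzed in the same way as the primary endpoint". Section 1.3.1 defines that way: "The primary analysis method is ANOVA with the treatment group, vehicle, and site, if more than one site, as main effects".

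**Room left open.** Section 1.3.2 continues: "Other statistical methods may also be used as deemed appropriate. The details will be provided in the SAP". Section 1.2.1 says that changes to the statistical methods made before unblinding "will be documented in the statistical analysis plan and will not require a protocol amendment".

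**The concern.** There are two linked gaps.

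First, the timing sentence contradicts the dosing time. Staff who follow its first half would collect a value about an hour after dosing. Staff who follow its second half would collect a true baseline. The text does not say which is meant.

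Second, the named model has no baseline term, and the plan does not say whether the STAI-6 response is the post-travel score or the change between readings. The first reading is collected but given no role.

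The second gap depends on the first. A pre-dose reading is a sound covariate, and leaving it out wastes precision without biasing the randomized comparison. A post-dose reading may already carry part of any drug effect, so adjusting for it or subtracting it would remove some of what the trial wants to estimate. Post-travel ANOVA, change score and ANCOVA also differ in precision, so the choice should be fixed before unblinding.

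**Working it through.** **Timing.** Take boarding as 0 minutes.

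- Dose: about −60 minutes.
- Reading before the dose: earlier than about −60 minutes.
- Reading at the beginning of travel: about 0 minutes or later.

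The two descriptions are about 60 minutes or more apart, and nothing in the public text reconciles them.

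**The plan's own figure.** The only power figure (section 1.1) concerns motion sickness severity: difference 0.8, SD 1.6, 75 per arm, two-sided alpha 0.05. The standardised effect is 0.8 / (1.6 × √(2/75)) = 3.06. Power is 86.5% by the normal approximation and 86.0% by the noncentral t, which matches the stated 86%. It says nothing about STAI-6; only the 75 per arm is used below.

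**Assumptions for STAI-6.** The documents give no SD, correlation or time course. Assume equal SDs at the two readings and a pre/post correlation ρ of 0.3, 0.5 or 0.7.

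**Precision if the reading is pre-dose.** Variance of the treatment effect relative to post-travel ANOVA is 1 − ρ² for ANCOVA and 2(1 − ρ) for change. The difference detectable at 80% power with post-travel ANOVA is (1.96 + 0.84) × √(2/75) = 0.457 SD. The other methods multiply this by the square root of their relative variance.

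| ρ | ANCOVA variance | ANCOVA interval width | Change variance | Detectable, ANCOVA | Detectable, change |
|---|---|---|---|---|---|
| 0.3 | 0.91 | 0.954 | 1.40 | 0.436 SD | 0.541 SD |
| 0.5 | 0.75 | 0.866 | 1.00 | 0.396 SD | 0.457 SD |
| 0.7 | 0.51 | 0.714 | 0.60 | 0.327 SD | 0.354 SD |

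ANCOVA intervals are 5% to 29% narrower than those from post-travel ANOVA. Change loses to post-travel ANOVA when ρ is below 0.5. ANCOVA is never worse than change, because 2(1 − ρ) − (1 − ρ²) = (1 − ρ)², which is not negative. It costs about one degree of freedom.

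**Some late readings.** Suppose a fraction m = 0.2 of first readings are post-dose and are replaced by the pooled mean. The variance reduction is (1 − m)ρ² = 0.8 × 0.09, 0.8 × 0.25 and 0.8 × 0.49, that is 7%, 20% and 39%.

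**All readings late.** Suppose every first reading is post-dose and already shows a fraction k of the final effect, with k from 0.25 to 0.5.

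- ANCOVA keeps 1 − ρk of the effect: 0.925 (ρ 0.3, k 0.25) down to 0.65 (ρ 0.7, k 0.5).
- Change keeps 1 − k: 0.75 down to 0.50.
- Post-travel ANOVA keeps all of it.

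**Simulation check.** 75 per arm, vehicle in the model, ρ 0.5, assumed true effect 0.4 SD.

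- All readings pre-dose: power about 67% for post-travel ANOVA, 79–80% for ANCOVA, 67% for change.
- 20% late and mean-imputed: ANCOVA estimate 0.402, power 76–77%, type I error 4.5–5.1%.
- All readings post-dose, k 0.5: estimates 0.40 for post-travel ANOVA, 0.30 for ANCOVA, 0.20 for change.

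**The case against.** The strongest reply is that this is loose wording plus detail deferred to the SAP. The clause placing the reading before dosing is the more specific anchor, and the beginning of travel may simply mean the start of the travel visit. The public text also cites a section 11.1.3 and an Appendix 20.1 that it does not contain, so a clear assessment schedule may exist elsewhere. The statistics section describes its methods only in general terms. Under the ANOVA it names, neither timing can bias the STAI-6 comparison; exposure to bias comes only with a method that uses the first reading.

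Much of this stands. A pre-dose reading was probably intended, the SAP may already settle the model, and there is no bias under the named ANOVA. The correlations, the 20% late fraction and k are all assumed, and nothing in the documents suggests that every reading was taken after dosing.

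Two things remain. When a questionnaire is given is an instruction to the site, so a SAP written later cannot settle it, and the SAP cannot choose a sound model without knowing it. Also, section 1.3.2 does name a method, and that method leaves out a value the trial already plans to collect. The risk created by using the reading is met by a rule that bars post-dose values from the model.

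The calendar also limits the remedy. The Synopsis gives first enrolment as December 2018 and a duration of four months, while the protocol is dated 18 March 2019. New timing text and clock times may therefore reach only the later subjects. The SAP statement is not limited in this way.

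**Conclusion.** The concern holds. The timing of the first STAI-6 conflicts with the stated dosing time, the named analysis has no baseline term, and the public text does not say whether or how the reading is used. It does not follow that the reading will certainly go unused.

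The practical loss is precision on one secondary objective. Under the equal-SD assumption it is small at ρ 0.3 (9% of variance) and material at 0.5 to 0.7 (25% to 49%). Bias is a conditional risk: it needs post-dose readings and an analysis that adjusts for or subtracts them. The primary MSSS analysis and its power are unaffected. This should be corrected because it is cheap to correct, but it does not threaten the trial's main result. Confidence is moderate, since the full schedule and a separate SAP are not in the public text.

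**What to change.** 1. Reconcile the Overall Design sentence so that the first STAI-6 is clearly pre-dose, leaving the dosing schedule as it is. Ask the sponsor to confirm when the reading was taken for subjects who have already travelled.
2. Record the clock time of the questionnaire and of dosing, if this is not already done.
3. State in section 1.3.2 or the SAP that the response is the post-travel STAI-6 score, analysed by ANCOVA on treatment and vehicle (and site if more than one) with pre-dose STAI-6 as covariate.
4. State that a reading timed after dosing is not used as a covariate. It is treated as a missing baseline and replaced by the mean of the valid pre-dose readings pooled across arms, so no subject is dropped. If readings turn out to have been post-dose in general, keep the post-travel ANOVA, which stays unbiased.

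The cost is low: one clarified sentence, two clock times and a short SAP statement. No assessment is added. Section 1.2.1 allows the change of method to be made in the SAP before unblinding without a protocol amendment.

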1. STATISTICS

1.1. Sample Size and Accrual

A sample size of up to 75 subjects per arm (150 total) will provide around 86% power to detect a 0.8 point difference in motion sickness severity between Tradipitant and Placebo, with the standard deviation of motion sickness severity assumed to be around 1.6.

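### Is the LTMSQ, described as a rating of the trip, wrongly tested as a symptom efficacy endpoint?

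*Combined protocol and SAP*

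**What the plan says.** The Overall Design part of the synopsis lists the questionnaires completed once travel has ended. The LTMSQ is introduced as a travel questionnaire for the subject to "assess the likelihood of their travel experience to induce motion sickness based on experience scored from 1-9 (LTMSQ"). The same sentence introduces the SDQ as "a questionnaire to record the duration of symptoms (SDQ").

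Secondary objective 2 in the synopsis reads: "To assess the effects of tradipitant 170 mg on the symptoms of motion sickness as measured by subjective parameter LTMSQ". The Statistical Methods part of the synopsis makes the MSSS the main measure, "with the other questionnaires serving as secondary endpoints". Section 1.3.2 adds: "The secondary endpoints from other questionnaires (MSAQ, SDQ, LTMSQ, STAI-6, PGI-S) will be analyzed in the same way as the primary endpoint". For the LTMSQ this means ANOVA with treatment, vehicle and, if there is more than one, site as main effects.

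The supplied text does not give the item wording or anchors of the LTMSQ, and does not say whether a high or a low score is the better result. Section 1.3.2 leaves further detail to the SAP. Section 1.2.1 says that changes in statistical method made before unblinding "will be documented in the statistical analysis plan and will not require a protocol amendment".

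**The concern.** The description and the use do not match on their face. A score for how provocative a journey was is a property of the journey. Both arms take the same kinds of trip, and randomisation should balance how rough those trips are. On that reading the expected difference between arms is zero even if the drug works well.

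The plan also seems able to separate constructs when it wants to. The SDQ is described by reference to symptoms, and the STAI-6 has its own anxiety objective. The LTMSQ gets neither treatment and is placed with the symptom measures.

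At stake is the reading of one secondary result. A null might be taken to show that symptoms did not improve, and a difference might be taken as direct proof that they did. The remedy that suggests itself is to remove the LTMSQ from the objectives and from section 1.3.2 and report it descriptively only.

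**Working it through.** **The plan's own power figure.** Inputs from section 1.1: 75 per arm, difference 0.8, SD 1.6. From section 1.2.1: two-sided alpha 0.05.

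- Standard error of the difference: 1.6 × √(2/75) = 0.2613.
- Noncentrality: 0.8 / 0.2613 = 3.062.
- Normal approximation: Φ(3.062 − 1.960) = Φ(1.102) = 0.865.
- Noncentral t, 148 df: 0.860.

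Both agree with the stated power of around 86%. That figure is for motion sickness severity. The plan gives no effect size or SD for the LTMSQ.

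**What a diluted effect would do.** Let k be the share of the planned standardised effect (0.8/1.6 = 0.5 SD) that carries over into the LTMSQ rating. The documents do not give k, so the range 0 to 1 is an assumption. Noncentrality is 3.062 × k. The last column is the chance of a significant result favouring tradipitant (t test, 148 df, two-sided 0.05).

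| k | Noncentrality | Chance |
|---|---|---|
| 0 | 0 | 2.5% |
| 0.25 | 0.765 | 11.5% |
| 0.5 | 1.531 | 33.0% |
| 0.75 | 2.296 | 62.6% |
| 1 | 3.062 | 86.0% |

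The table shows that an LTMSQ null is compatible with the full planned effect on symptoms. It shows little else. Running k from 0 to 1 must produce everything between the one-tail error rate and the planned power. The same table could be drawn for the MSAQ, SDQ or PGI-S, because section 1.1 covers none of them. It is an illustration and not evidence about this instrument.

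**What each reading implies.**

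1. *The subject rates the trip and ignores how they felt.* The expected difference is zero (k = 0). The test errs in favour of the drug 2.5% of the time, which is the nominal rate. The endpoint is uninformative but misleads no more often than any other null endpoint.
2. *The subject answers from how they felt on the trip.* The rating then carries symptom information, and objective 2 describes it fairly.
3. *The subject judges this trip against past travel.* The result falls between the first two, depending on how far present symptoms colour the comparison.

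The phrase about experience in the Overall Design text allows all three. In each, dosing is randomised and blinded and the rating comes after travel, so a genuine difference between arms is caused by treatment. A drug for motion sickness would most plausibly move the rating through felt symptoms. A chance difference in trips would affect the MSSS as well, and the significance level already allows for it.

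**The SDQ contrast.** Of the instruments assigned to symptom objectives, only the SDQ is described in that sentence by reference to symptoms. The MSSS, MSAQ and PGI-S are simply named there. One instrument does not establish a pattern of wording that leaves the LTMSQ out.

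**The case for a change.** The strongest case for a change is that the mismatch lies in the objective itself, and specifying a model in the SAP cannot alter what an instrument measures. Uncertainty about what an efficacy endpoint captures is a reason to resolve it before unblinding. The change would leave data collection as it is, and section 1.2.1 allows a revised analysis without an amendment.

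Part of this stands. As described, the LTMSQ is at most indirect evidence on symptoms, and a null on it says little. It would also be a poor covariate, because it is rated after dosing, but the plan does not propose that use.

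The step from there to removal does not stand. It would delete an objective on the strength of one clause in a synopsis, without sight of the questionnaire. The replacement label, perceived provocativeness of the travel, is no better established in the text than the sponsor's own. The allowance in section 1.2.1 covers statistical methods and does not mention objectives. The protocol is marked final on 03 18 2019, while the synopsis gives first enrolment in December 2018 and a duration of four months, so the edit would come late. No other result would change.

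**Conclusion.** No change to the plan follows. The description of the LTMSQ and its use as a symptom endpoint are not fully aligned, but the text does not show that the instrument fails to capture symptoms, and the planned test is valid as a comparison of randomised arms. What is missing is a statement of what the score measures and which direction is favourable. An analyst holding the questionnaire will have to settle that to label the table, and the SAP is the place to record it.

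The scope is one of five secondary questionnaires. The MSAQ, SDQ and PGI-S address symptoms independently of it, and the primary MSSS analysis, the sample size and the power (86.0% by the t test) are untouched. Removing the LTMSQ from the efficacy list would be a debatable trade: it avoids a possible misreading of a null and gives up a result that may carry symptom information. Reading the LTMSQ only as support for the MSSS achieves the same protection.

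This rests on two assumptions: that the blind holds, and that the questionnaire's wording leaves some room for felt symptoms to influence the answer. If it leaves none, the endpoint is uninformative, with a false-positive rate no higher than the nominal one.

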1. STATISTICS

1.1. Sample Size and Accrual

A sample size of up to 75 subjects per arm (150 total) will provide around 86% power to detect a 0.8 point difference in motion sickness severity between Tradipitant and Placebo, with the standard deviation of motion sickness severity assumed to be around 1.6.

1.2. Statistical Methods and Analysis Plan

1.2.1. General

This section describes the planned statistical analyses in general terms. A complete description of the methodology will be specified in a statistical analysis plan (SAP), which will be finalized prior to unblinding. Any changes in the statistical methods described in this protocol that occur prior to unblinding will be documented in the statistical analysis plan and will not require a protocol amendment.

Statistical hypothesis testing will be performed at two sided alpha level of 0.05. For continuous variables, population size (N for sample size and n for available data), the mean, the standard deviation (SD), the median, the minimum and maximum values will be tabulated. For categorical variables, population size and frequencies in each category will be tabulated.

